**Figure 3. Frequencies of a subset of COGA participants' alcohol-influenced aggression scores.**

heritability of  $h^2 = 0.2$ , a type I error rate of 0.05, and a variance of SNP-derived genetic relationships of .00002, suggested that 80% power for the proposed GCTA can be obtained with 4,430 participants. The [discovery] sample far exceeds this sample size at over [31,000] participants. GWAS power analyses, implemented via the GWAS.PC v1.0 package for R statistical software were also performed to determine the minimum effect size (in units of % variance explained) that [the discovery sample could detect with 80% power. Calculations were based on the planned detection of multiple, additive SNP markers, an alpha level of .05, and a minor allele frequency of 0.05, revealing that the proposed GWAS is able to detect effect sizes of 0.09% variance-explained and larger. However, this is likely an optimistic assessment as this power analysis did not account for the moderating effects of ethnicity/race and the genetic relatedness of participants (yet recent research has indicated that GWAS power is not significantly affected by underlying genetic relationships between participants).]

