**Genome-wide association study (GWAS).** After the GCTA, GWAS will be used to identify single nucleotide polymorphisms (SNPs) and clusters of SNPs that are significantly associated with alcohol-influenced aggression. Due to the skewness of the alcohol-influenced aggression scores (see Figure 3), quasi-Poisson regression analyses will be used to accommodate such a distribution using the Bioconductor v2.1 package and SNPTEST v2.5. Specifically, alcohol-influenced aggression scores will be regressed onto principal components of the available SNPs using an additive model, excluding non-autosomal SNPs, with demographics factors as covariates. Due to racial stratification, separate GWAS will be performed for participants of African, American, East Asian, European, South Asian, and Mixed Race descent. Participants will be empirically assigned to these ancestral super-populations using the 1KGP population base and the Mahalanobis' distance between each population. I will meta-analyze these separate sets of GWAS findings METAL v3.0^32, which will produce meta-analytic '% variance explained' effect size estimates and  $p$  values for each SNP. [In addition to this meta-analytic approach, I will test for gene-by-race/ethnicity moderation using a kernel-machine approach to estimate whether each SNP's association with alcohol-influenced aggression varies across the discovery sample's diverse racial/ethnic groups, using the Robust Joint Tests package.] After correction for genetic inflation and weighting based on sample size, I will calculate polygenic risk scores for alcohol-influenced aggression [based on SNPs meeting increasingly stringent significance thresholds: .5, .4, .3, .2, .1, .05, .01, .001, .0001. The threshold that maximizes the variance explained ( $R^2$ ) in alcohol-related aggression will be used for risk score calculation.] Using an additive approach, I will sum across the number of alleles that are significantly linked to the phenotype, weighted by their respective effect size estimates from the GWAS. For example, if the A allele (versus the corresponding G allele) of a given SNP is significantly associated with greater alcohol-influenced aggression, then each copy of the A allele will be initially coded as +1 (GG = 0, GA = 1, AA = 2). These scores will then be multiplied by the GWAS effect size estimate for that given SNP. This polygenic risk scores will capture aggregate genetic risk for alcohol-influenced aggression in a manner that represents the current state of the field.

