#### Potential Problems and Alternative Strategies

The proposed GWAS on the [discovery] sample may not yield any statistically-significant SNPs that are associated with alcohol-influenced aggression. If this is the case, polygenic risk scores will be obtained from the largest GWAS projects for both aggression (the EAGLE consortium^37) and alcohol misuse (Psychiatric Genomics Consortium^38). An alcohol-influenced aggression risk score will be computed by multiplying the aggression and alcohol misuse polygenic risk scores with one another, to statistically simulate the interactive effect of these genetic dispositions. There is a current push in genomics research for sample sizes that are unattainable by any individual investigator (e.g.,  $N > 50,000$ ). The proposed research outlined in the [discovery and replication] datasets are admittedly underpowered to detect a complex phenotype such as alcohol-influenced aggression. However, the proposed research activities will provide invaluable training that will be employed in well-powered datasets throughout my career as an alcohol investigator.

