#### Phase I - Replication in S4S Sample

Participants. At the outset of each academic year, incoming first-year VCU undergraduates are invited to participate in the S4S project via an online survey, and they have the option to provide a saliva sample that will be genotyped. Compensation is \$10. From 2011-2014, S4S has enrolled six consecutive cohorts (68% average enrollment from incoming freshman, average cohort  $N = \sim 2,500$ ). Of those individuals who completed the initial online component, 97% provided a saliva sample for genotyping. Participants in the sample reflect general demographics among VCU students, which are relatively diverse (40% male, 60% female; 51% White, 19% African American, 15% Asian, 6% Hispanic/Latino, and 9% other/multiracial/unknown). Increasing freshman class sizes have magnified the S4S cohort sizes in recent years to approximately 3,300 participants per cohort.

Genotyping and imputation. Genotyping is performed at Rutgers University Cell and DNA Repository (RUCDR) using the Affymetrix BioBank array. The 653,000 gene variants included in this array contain 296,000 common GWAS framework variants for imputation as well as 357,000 functional variants. Quality control uses AffyPipe analysis pipeline to exclude Off Target Variants, SNPs missing > 5% of genotypes, samples missing > 2% of genotypes, and SNPs missing > 2% of genotypes after sample filtering. Samples will be imputed to 1000 Genomes using SHAPEIT and then IMPUTE2.

Phenotype measures. The same SSAGA questions from the [discovery samples] about alcohol-influenced aggression will be added to the existing online survey administered to all new S4S participants at the onset of their participation. The S4S online survey already includes demographic assessments. These surveys will be administered in the fall of 2018, 2019, and 2020.

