#### Feasibility

This first phase of Aim II builds upon the already successful and ongoing S4S project, by simply adding a short online survey to the existing S4S battery of questionnaires. However, undergraduates at VCU differ from the [diverse members of the discovery sample] in ways that may suppress the amount of alcohol-influenced aggression among the S4S sample (e.g., lower levels of alcohol misuse and dependence). A pilot sample of VCU undergraduates were asked about their aggressive behavior and whether it occurred in the context of

alcohol misuse or not. Of the 166 female and male participants surveyed, 53.6% indicated that they had participated in a physical fight in the past 5 years (30.1% had been in more than 1 fight). Of those who had previously fought, 38.2% participated in this fight under the influence of alcohol. These initial estimates suggest that 1 out of 5 VCU undergraduates (i.e., 20.48%) have perpetrated a substantial act of physical aggression under the context of alcohol misuse. This prevalence rate indicates that the much larger pool of potential S4S participants is likely to exhibit alcohol-influenced aggression at a sufficient rate to test associations with polygenic risk scores.

Power analysis. The expected S4S sample size of 10,000 students will provide 80% power to detect a genome-wide effect of 0.35% variance explained in alcohol-influenced aggression, or larger. [The S4S GWAS is likely to be under-powered, yet performing this replication GWAS will serve as a valuable training in how to collect genomic data and use it to replicate previous GWAS results.]

Potential Problems and Alternative Strategies. The S4S sample GWAS may not replicate the profile of SNPs found in the [discovery] sample, as the S4S sample is smaller and is comprised of undergraduate students. However, replication is a crucial step in genomic science and this is as important training experience.

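### The two GWAS detectable effects (0.09% at N = 31,123 and 0.35% at N = 10,000) cannot share one basis at the stated sample sizes, and 0.09% does not follow from a per-SNP alpha of .05

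*Combined protocol and SAP*

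**What the plan says.** The Power analysis paragraph for the discovery sample (under Feasibility) works at 80% power. It describes its basis as the "planned detection of multiple, additive SNP markers, an alpha level of .05, and a minor allele frequency of 0.05", and ends by "revealing that the proposed GWAS is able to detect effect sizes of 0.09% variance-explained and larger". It does not say whether .05 applies to each SNP or to the whole family of tests, or how many markers are tested jointly. The discovery N is 31,123, which is the sum of the five studies in Table 1.

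The Power analysis paragraph for Phase I says: "The expected S4S sample size of 10,000 students will provide 80% power to detect a genome-wide effect of 0.35% variance explained". It gives no alpha, degrees of freedom or marker model. The Phase I Analytic Plan applies the discovery GWAS and risk-score procedures to S4S.

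On the S4S sample size, the Participants paragraph gives an average cohort of about 2,500 and says that larger freshman classes have "magnified the S4S cohort sizes in recent years to approximately 3,300 participants per cohort". On timing, the plan says: "These surveys will be administered in the fall of 2018, 2019, and 2020".

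Under Potential Problems and Alternative Strategies for the discovery sample, the plan anticipates that the GWAS "may not yield any statistically-significant SNPs that are associated with alcohol-influenced aggression". In that case a product of two external risk scores is used. No p-value cut-off is attached to that condition. The GWAS paragraph of the Analytic Plan does list p-values, from .5 to .0001, but these are for building the score "based on SNPs meeting increasingly stringent significance thresholds".

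**The concern.** When two power statements use the same method at the same power, the detectable variance explained should fall almost exactly in inverse proportion to N. Here the ratio of sample sizes is 31,123 / 10,000 = 3.11, while the ratio of detectable effects is 0.35 / 0.09 = 3.89. The one alpha that is printed also does not lead to 0.09% under its plainest reading.

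A reader therefore cannot tell what size of SNP effect either GWAS can detect, or compare discovery with replication. If the intended level is a conventional genome-wide one, both printed effects are too favourable for 80% power. The missing level has a secondary consequence: the switch to the fallback score depends on whether any SNP is significant, and the plan does not define that.

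**Working it through.** **Inputs.** Discovery: N = 31,123, 80% power, alpha .05, effect 0.09%. S4S: N = 10,000, 80% power, effect 0.35%. Minor allele frequency drops out because effects are in variance explained.

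**Formula.** For an additive 1-df test, NCP = N × R² / (1 − R²). At 80% power the required NCP is (z for alpha + 0.8416)², so the detectable R² = NCP / (N + NCP).

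**Step 1: the plan's own figure.** With two-sided .05 per SNP, NCP = (1.960 + 0.8416)² = 7.85.
- Discovery: 7.85 / (31,123 + 7.85) = 0.025%, against the printed 0.09%.
- S4S: 7.85 / (10,000 + 7.85) = 0.078%, against the printed 0.35%.
- At that alpha, 0.09% at N = 31,123 would have 99.96% power, not 80%.

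As a control, the GCTA figure in the same paragraph does reproduce. With h² = 0.2, variance .00002 and N = 4,430, the standard error is √(2 / (4,430² × .00002)) = 0.0714. Then 0.2 / 0.0714 − 1.960 = 0.84, which is 80.0% power.

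**Step 2: do the two figures share a basis?** For one alpha, df and marker model, the NCP must be equal in both samples.

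| Sample | Printed effect | NCP | NCP over rounding limits |
|---|---|---|---|
| Discovery, 31,123 | 0.09% | 31,123 × 0.0009 / 0.9991 = 28.0 | 26.5 to 29.6 (0.085% to 0.095%) |
| S4S, 10,000 | 0.35% | 10,000 × 0.0035 / 0.9965 = 35.1 | 34.6 to 35.6 (0.345% to 0.355%) |

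The ranges do not overlap. As 1-df two-sided levels they correspond to about 8.5e-6 (4.3e-6 to 1.7e-5) for discovery and 3.7e-7 (2.9e-7 to 4.6e-7) for S4S.

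**Step 3: can another marker model rescue the pair?** Several unstated settings come near 0.09% at N = 31,123, but none gives 0.35% at N = 10,000.

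| Setting | N = 31,123 | N = 10,000 |
|---|---|---|
| .05 over about 5,900 tests, 1 df | 0.090% | 0.280% |
| Joint test of 42 SNPs at .05 | 0.090% | 0.280% |
| At least one of 3 SNPs at 5e-8 | 0.088% | 0.274% |

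In the other direction, one-sided .05/296,000 gives 0.352% at 10,000 but 0.113% at 31,123.

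**Step 4: what N would reconcile them?**
- S4S: N = 28.04 × 0.9965 / 0.0035, about 8,000 (7,430 to 8,550 with rounding).
- Discovery: N = 35.12 × 0.9991 / 0.0009, about 39,000 (36,400 to 41,900), which is above the 31,123 available.
- Three S4S survey years give 3 × 2,500 = 7,500 to 3 × 3,300 = 9,900. About 8,000 lies inside that span, but the power statement says 10,000.

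**Step 5: illustration on a common basis.** Assume 5e-8 per SNP (not in the documents) and a pooled 1-df linear test. NCP = (5.451 + 0.8416)² = 39.60.
- Discovery: 39.60 / (31,123 + 39.60) = 0.127%. Power at 0.09% is Φ(√28.04 − 5.451) = Φ(−0.156) = 44%.
- S4S: 39.60 / (10,000 + 39.60) = 0.394%. Power at 0.35% is Φ(√35.12 − 5.451) = Φ(0.475) = 68%.

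**The case against.** The strongest reply is that equal NCP is required only if the two calculations share their settings, and the plan never says that they do. The S4S paragraph gives no alpha or marker model. The instruction to use the same procedures concerns the analysis, not the power settings. The S4S effect is also called genome-wide, which may signal a different threshold or even a different quantity. This stands as far as it goes: a reader might infer that the software output or the arithmetic is wrong, and the documents do not support that. Each figure can be matched alone under some unstated setting. A reader might also infer that the figures conflict at any sample size. They do not; an S4S N near 8,000 would reconcile them.

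The plan is also candid about power. It calls the discovery figure likely optimistic, both datasets underpowered, and the S4S GWAS likely under-powered. But the stated reasons for optimism are ancestry and relatedness. None of these remarks addresses alpha or the mismatch.

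On the fallback score, a reader might infer that chance hits at .0001 would prevent it from ever applying, so that the undefined cut-off determines who is scanned. The documents do not support that. The .5 to .0001 values are for score inclusion, and analysts would ordinarily supply a conventional genome-wide level. Nor can chance hits be counted from "The 653,000 gene variants included in this array": that is the S4S array before imputation, and the tested number in neither GWAS.

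**Conclusion.** The point holds as a correction of stated numbers. At the stated sample sizes and 80% power, 0.09% and 0.35% cannot come from one alpha, df and marker model, even after rounding. On the basis behind 0.09%, S4S at 10,000 would detect about 0.28% (0.26% to 0.30%). On the basis behind 0.35%, discovery would detect about 0.113% (0.111% to 0.114%). Separately, .05 read per SNP at 1 df gives 0.025% rather than 0.09%.

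Whether alpha, marker model or N is responsible cannot be determined from the documents. The incompatibility itself does not depend on which alpha or marker model is chosen, provided it is shared. The 0.127% and 0.394% do depend on the assumed 5e-8. They are approximations, because they ignore the planned quasi-Poisson models and the ancestry-stratified meta-analysis. They also keep N = 31,123. The GCTA paragraph excludes pairs related at second-cousin degree or closer from later analyses; if that covers the GWAS, the discovery figure worsens in near-inverse proportion to the N lost, which the plan does not give.

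No sample size rests on either figure. The undefined level for a significant SNP is a secondary clarification.

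**What to change.** In the two Power analysis paragraphs:
- Declare one per-SNP significance level for both GWAS, saying whether the printed .05 is per SNP or family-wise.
- State the degrees of freedom or marker model.
- State the N actually used for each sample: for discovery, after any exclusion of relatives; for S4S, the number expected to be genotyped and surveyed over the three years.
- Restate both detectable effects at 80% power on that basis. If the two calculations were meant to differ, say so and give the settings of each.

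As a secondary clarification, use the declared level under Potential Problems and Alternative Strategies to define when no SNP counts as significant. Add that the p-values from .5 to .0001 in the Analytic Plan govern only entry into the score.

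The cost is about three sentences and a rerun of the two power calculations. If a genome-wide level is chosen, the stated detectable effects become less favourable. No extra participants are needed.

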#### Potential Problems and Alternative Strategies

The proposed GWAS on the [discovery] sample may not yield any statistically-significant SNPs that are associated with alcohol-influenced aggression. If this is the case, polygenic risk scores will be obtained from the largest GWAS projects for both aggression (the EAGLE consortium^37) and alcohol misuse (Psychiatric Genomics Consortium^38). An alcohol-influenced aggression risk score will be computed by multiplying the aggression and alcohol misuse polygenic risk scores with one another, to statistically simulate the interactive effect of these genetic dispositions. There is a current push in genomics research for sample sizes that are unattainable by any individual investigator (e.g.,  $N > 50,000$ ). The proposed research outlined in the [discovery and replication] datasets are admittedly underpowered to detect a complex phenotype such as alcohol-influenced aggression. However, the proposed research activities will provide invaluable training that will be employed in well-powered datasets throughout my career as an alcohol investigator.

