#### Discovery Sample from dbGaP

The GWAS discovery sample ( $N = 31,123$ ) will be drawn from five ongoing and completed, multisite studies on the genetic basis of substance dependence and related behavior, available via dbGaP (Table 1).

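### The switch to a fallback polygenic score depends on an undefined absence of significant SNPs, which does not show whether the planned direct score predicts

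*Combined protocol and SAP*

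**What the plan says.** The GWAS paragraph of the discovery-sample Analytic Plan builds the direct score "based on SNPs meeting increasingly stringent significance thresholds: .5, .4, .3, .2, .1, .05, .01, .001, .0001". The threshold giving the highest R² "in alcohol-related aggression will be used for risk score calculation". The same paragraph then describes the scoring differently: "I will sum across the number of alleles that are significantly linked to the phenotype".

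The discovery-sample section Potential Problems and Alternative Strategies says the GWAS "may not yield any statistically-significant SNPs that are associated with alcohol-influenced aggression". It continues: "If this is the case, polygenic risk scores will be obtained from the largest GWAS projects for both aggression" and, from a second consortium, alcohol misuse. "An alcohol-influenced aggression risk score will be computed by multiplying the aggression and alcohol misuse polygenic risk scores with one another". No significance level is attached to this condition. The section does not say that the direct score would be kept, compared with the product, or tested before being replaced. On how probable the event is, it says only that the "datasets are admittedly underpowered to detect a complex phenotype such as alcohol-influenced aggression".

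Recruitment and Screening, under Phase II, says the low- and high-risk MRI groups are selected on scores from the discovery GWAS. It does not mention the fallback.

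**The concern.** The trigger and the score measure different things. A score summing thousands of SNPs at p<.5 can predict although no single SNP stands out, so having no significant SNP does not show that the score has failed. The contingency plan nevertheless treats it as the reason to abandon the score.

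The undefined significance level makes the rule ambiguous. Under one reading the fallback cannot practically be reached. Under another it can be reached when the direct score still carries signal.

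What is at stake is which score defines the 202-person MRI sample and so what Hypothesis 4 tests. A switch would move from a score trained on the target phenotype to a product of scores for two other phenotypes, with no look at the performance of either.

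**Working it through.** **1. The plan's own figures.** The discovery power paragraph gives h²=0.2, alpha .05, variance of genetic relationships .00002 and 80% power for GCTA. N = (z₀.₉₇₅ + z₀.₈₀) × √(2/.00002) / h² = (1.960 + 0.842) × 316.23 / 0.2 = 4,430, which matches the stated 4,430.

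For the GWAS it states 0.09% variance explained at alpha .05 and 80% power. With the one-SNP formula, q² = (z₁₋α/₂ + z₀.₈₀)² / N and N = 31,123:
- alpha .05, two-sided: 7.849 / 31,123 = 0.025%
- alpha 5e-8, two-sided: (5.451 + 0.842)² / 31,123 = 0.127%

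A value of 0.09% would need a two-sided alpha of about 8.6e-6. The plan mentions a multi-marker calculation and gives no number of tests, so the mismatch does not prove an error, and the point does not rest on it. It does mean that the cut-off intended by the contingency plan cannot be recovered from the power paragraph.

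**2. Trigger at the stated alpha.** The documents give no SNP count for the discovery arrays. As an illustration, take the 296,000 common framework variants on the Spit for Science array as independent and null. Expected passes at .05 are 296,000 × .05 = 14,800. The chance of none is .95^296,000, about 10^−6,594. The fallback would practically never apply.

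**3. Trigger at an assumed 5e-8.** Power for one SNP is Φ(√(N·q²) − 5.451).
- q² = 0.09%: Φ(5.293 − 5.451) = 44%
- q² = 0.05%: Φ(3.945 − 5.451) = 6.6%

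Whether there is any hit then depends on how many SNPs share the heritability.

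**4. Can no hits and a predictive score occur together?** The expected R² of a score using all SNPs is h² / (1 + M/(N·h²)). M = 60,000 effective SNPs is an assumption. h² = 0.2 is the plan's power input, and h² = 0.1 is its benchmark for substantial heritability. N = 15,000 is an assumed size after exclusions.
- h²=0.2, N=31,123: 0.2 / (1 + 60,000/6,224.6) = 1.88%
- h²=0.1, N=31,123: 0.1 / (1 + 60,000/3,112.3) = 0.49%
- h²=0.2, N=15,000: 0.2 / (1 + 60,000/3,000) = 0.95%
- h²=0.1, N=15,000: 0.1 / (1 + 60,000/1,500) = 0.24%

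A simulation used 60,000 independent SNPs, normal effects and 40 runs per scenario. R² is out of sample and averaged over all runs, not only those without a hit:

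| h² | N | Causal SNPs | Runs with no SNP at p<5e-8 | R² of p<.5 score |
|---|---|---|---|---|
| 0.2 | 31,123 | 1,000 | 0% | 1.93% |
| 0.2 | 31,123 | 5,000 | 25% | 1.90% |
| 0.2 | 31,123 | 10,000 | 80% | 1.85% |
| 0.2 | 31,123 | 60,000 | 100% | 1.75% |
| 0.2 | 15,000 | 10,000 | 100% | 0.94% |
| 0.1 | 31,123 | 10,000 | 97.5% | 0.48% |
| 0.1 | 15,000 | 60,000 | 100% | 0.23% |

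In the two rows with 60,000 causal SNPs, and in the h²=0.2, N=15,000 row, every run lacked a hit, so the average there is the no-hit value. No hits and a non-zero R² can therefore coexist. With few causal SNPs and the full sample, the trigger does not fire.

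**The case against.** A reader might infer that the plan expects a null GWAS and would throw away a usable score. The documents do not support that. They say a null result may happen and that the samples are underpowered. They do not call it likely, and the power paragraph claims 80% power at 0.09%.

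Nor do they fix the cut-off at 5e-8. The GWAS paragraph calls its own inclusion limits significance thresholds. If the contingency plan uses the word in that sense, nothing is ever discarded. This stands, and it is why the undefined trigger is part of the point.

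A reader might also infer that the direct score would be well powered in Spit for Science. That is not shown. The R² values assume full transfer, yet the plan runs ancestry-specific GWAS, the student sample is 51% White, and the plan says the students differ from the discovery participants. In Phase II the outcome is a laboratory noise blast. Suppose the groups were the top and bottom 5% of scores with 99 each, and the score predicted that outcome equally well. Power would then be about 53% at R²=0.5%.

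Finally, nothing shows that the product score predicts worse, because the accuracy of the external scores is not in the documents. Hypothesis 3, on specific polymorphisms, also goes unsupported without hits whichever score is used. Both points stand. They limit the claim to the decision rule, which switches scores without comparing or testing either.

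**Conclusion.** The contingency rule should be changed. As written it is either practically inert (alpha .05 unadjusted) or keyed to the wrong quantity (a strict cut-off), and the plan does not say which. The mismatch with the score's p<.5 to p<.0001 thresholds follows from the text alone.

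The size of what could be discarded is illustrative. It is R² of about 1.8–1.9% in highly polygenic scenarios at h²=0.2 and N=31,123, and about 0.2–1% at lower h² or N, before any loss on transfer. These figures rest on an assumed 5e-8 cut-off, 60,000 independent SNPs and normal effects. They show that the direct score may still predict when there are no hits. They do not show that a null result is probable or that the score would be adequate for Aim 4.

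**What to change.** Replace the trigger with the direct score's out-of-sample performance. Use the discovery score unless it fails to predict alcohol-influenced aggression in a leave-one-study-out analysis of the five discovery studies, and only then use the product score. Specify in advance:
- one pooled test across the held-out studies, with its level; report the pooled R² as well, because a .05 test at these sample sizes would pass a trivial R²
- choice of the p-threshold within the training studies only
- removal from each held-out study of participants shared with, or related to, those in the training studies; COGA, COGEND and FSCD carry one dbGaP ID in Table 1, so overlap needs checking

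In the GWAS paragraph, delete the requirement that scored alleles be significantly linked to the phenotype. In Recruitment and Screening, state that groups are formed on whichever score this rule selects.

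The cost is wording and one extra analysis of data already in the plan. Table 3 puts discovery analysis in Years 1–2 and imaging in Years 3–4, so it can precede recruitment. Training samples shrink in each fold, most when COGA is held out (31,123 − 17,783 = 13,340), so the test is somewhat conservative for the full-sample score.
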